5.2.3.2. Supplementary Analysis

Posterior probability of ORR > 25% for Individual Tumor Histologies

As a supplementary analysis, the posterior probability of $ORR > 25\%$ for each individual tumor histology will also be evaluated. This will provide additional evidence of the contribution of each individual tumor histology that didn't meet the futility criteria in the Broad Panel Cohort to the overall result of the pooled primary efficacy analysis. More details are discussed in the [Appendix A.3](#).

Analysis for Treated Population including Tumor Histologies Deemed Futeile

Analysis with all tumor histologies including those deemed futile during the three interim analyses as well as the final futility assessment will also be conducted. This analysis is applicable only when there are tumor histologies deemed futile or excluded from the primary efficacy analysis.

Analysis of Subjects Assessed by RECIST v1.1 or RANO criteria

A supplementary efficacy analysis may be provided for Treated Population in the Broad Panel Cohort separating subjects assessed by RECIST v1.1 criteria and by RANO criteria for tumor response.

5.2.3.3. Sensitivity Analysis

Analysis with Response-evaluable Population

A sensitivity analysis of ORR assessed by IRC may be provided on the pooled data of all tumor histologies that did not meet the futility for the Response-evaluable Population in the Broad Panel Cohort.

Analysis with Subjects Considering Molecular Eligibility

Sensitivity efficacy analysis of ORR assessed by IRC may be performed for Treated Population in the Broad Panel Cohort excluding patients

- without an eligible FGFR alteration (e.g., a patient enrolled with FGFR2-L551F mutation)
- with only known or suspected FGFR germline mutations (FGFR2-A97T, FGFR3-R399C, FGFR3 F384L, FGFR3-A500T, FGFR3-P572A, FGFR3-P572L)

- with only FGFR fusions with a 5'-partner (Partner gene is listed first and FGFR gene is second, eg GENE-FGFR or KLK2-FGFR2), as oncogenic potential of FGFR fusions with a 5'-partner is less well understood as compared to those fusions with 3'partner
- with gatekeeper/resistance FGFR alterations (FGFR1-V561; FGFR2-V564; FGFR3-V555; FGFR4-V550; FGFR1-N546; FGFR2-N549; FGFR3-N540 and FGFR4-N535)
- or with exclusionary co-alterations (For NSCLC subjects only - pathogenic somatic mutations in EGFR or BRAF V600E, KRAS, or any gene fusions in the following genes: ALK, ROS1, or NTRK. For colorectal subjects only – pathogenic somatic mutations in BRAF, KRAS, NRAS and PIK3CA as specified in the protocol)

Analysis Pooling Cholangiocarcinoma Expansion Cohort and/or Pediatric Cohort

A sensitivity efficacy analysis may be provided on the pooled data of Treated Population in the Broad Panel Cohort, Treated Population in the Cholangiocarcinoma Expansion Cohort, and/or Treated Population in the Pediatric Cohort that meet the molecular eligibility for the Broad Panel Cohort.

5.2.3.4. Subgroup Analysis

Subgroup analyses for the ORR by IRC will be conducted for each subgroup (Section 2.3) within the Treated Population, respectively.

5.3. Major Secondary Endpoints

5.3.1. ORR assessed by Investigator

The proportion of subjects in the primary cohort who achieve a CR or PR based on RECIST v1.1 or RANO as assessed by Investigator. The response rate and its two-sided 95% Clopper-Pearson CI will be provided.

Similar analyses as listed the in 5.2.3.1 for the primary endpoint may be conducted as well.

5.3.2. Duration of Response (DOR)

Definition

Duration of response will be analyzed for subjects with the BOR of CR or PR and is defined as the interval between the date of initial documentation of a response and the first documented evidence of PD or death due to any cause. Subjects who are progression-free and alive or have unknown status will be censored at the last tumor assessment. Subjects who had disease progression or death event but started a subsequent anti-cancer therapy before disease progression or death event will be censored at the last disease assessment before the subsequent therapy. Subjects with death or progressive disease after more than one missing DEs will be censored at the date of the last tumor assessment without documented progressive disease.

Analysis method

DOE based on both IRC assessment and investigator assessment will be provided. DOE will be presented with descriptive summary statistics. Kaplan-Meier method will be used for evaluation, if there are sufficient data.

5.3.3. Disease Control Rate (DCR)

Definition

DCR is defined as the proportion of subjects who achieve a best response of CR, PR, or SD based on RECIST v1.1 or RANO (by IRC and Investigator).

For interim analysis, the definition of DCR will also be considered as the proportion of subjects who achieve a best response of CR, PR, uCR, uPR or SD based on RECIST v1.1 or RANO.

Analysis method

The DCR and its two-sided 95% Clopper-Pearson confidence interval will be provided based on both IRC assessment and investigator assessment.

5.3.4. Clinical Benefit Rate (CBR)

Definition

CBR is defined as the proportion of subjects who achieve a best response of CR, PR, or durable SD (defined as a duration of at least 4 months) based on RECIST v1.1 or RANO (by IRC and Investigator).

For interim analysis, the definition of CBR will also be considered as the proportion of subjects who achieve a best response of CR, PR, uCR, uPR or durable SD (defined as a duration of at least 4 months) based on RECIST v1.1 or RANO.

Analysis method

The CBR and its two-sided 95% Clopper-Pearson CI will be provided based on both IRC assessment and investigator assessment.

5.3.5. Progression-free Survival (PFS)

Definition

Progression-free survival is defined as the duration from the date of the first dose of erdafitinib until the date of first documented evidence of progressive disease or death due to any cause, whichever occurs first. Subjects who are progression-free and alive or have unknown status will be censored at the last disease evaluation. Subjects with no baseline or no post-baseline disease evaluation will be censored at the date of first dose. Subjects who had a disease progression or death event after having started a subsequent anti-cancer therapy will be censored at the last disease evaluation before the subsequent therapy. Subjects with death or progressive disease after more than one missing disease evaluations will be censored at the date of the last disease evaluation without documented progressive disease.

Analysis method

PFS based on both IRC assessment and investigator assessment will be presented with descriptive summary statistics; Kaplan-Meier method will be used for evaluation, if there are sufficient data.

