8.2. Efficacy Assessments

For adult subjects, disease assessments will be performed every 6 weeks (every 2 cycles) for the first 12 months and then every 12 weeks (every 4 cycles) thereafter (\pm 7-day window), as outlined in the Schedule of Activities.

For pediatric subjects, disease assessments will be performed every 12 weeks (every 4 cycles, \pm 7-day window), as outlined in the Schedule of Activities. For subjects with low-grade gliomas where a lower frequency of imaging is sufficient, a 24-week frequency (\pm 7 days) may be adopted after a minimum of 12 months with the sponsor's approval. If a response (partial response or complete response) is observed, an additional scan for confirmation is required 4 to 8 weeks (\pm 7-day window) after the first scan showing the response.

Assessment of responses for solid tumors will be performed according to RECIST (Version 1.1) or RANO guidelines by investigators. For subjects who discontinue study drug before disease progression, tumor assessments should continue as described in Section 8.1.2.

More frequent radiological assessments are allowed, if clinically indicated/desirable. Identical methodology (computed tomography [CT] scan or magnetic resonance imaging [MRI]) should be used for disease assessment at baseline, and throughout the course of the study, to characterize each identified and reported lesion to document disease status. Ultrasound, fluorine 18-fluorodeoxyglucose positron emission tomography (FDG-PET), and plain x-rays are not acceptable methods of evaluating disease response in the absence of CT or MRI scans.

If symptomatic deterioration (based on global deterioration of health status) occurs without documentation of radiographic progression or disease progression as measured by skin lesion assessment and photography if applicable, the clinical findings used to make this determination must be specified in the eCRF and documented in the source documents. Every effort should be made to document the objective progression even after discontinuation of treatment for symptomatic deterioration. Tumor response will be reported by the investigator in the eCRF.

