9.4.2. Secondary Efficacy Endpoints

- ORR assessed by investigator: the proportion of subjects who achieve a CR or PR based on RECIST v1.1 or RANO as assessed by investigator.
- DOR: the duration from the date of initial documentation of a response to the date of first documented evidence of progressive disease (or relapse for subjects who experience CR during the study), or death, whichever comes first, for subjects. Data from subjects who are progression-free and alive or have unknown status will be censored at the last tumor assessment
- DCR: the proportion of subjects with CR, PR or SD
- CBR: the proportion of subjects with CR, PR or durable SD (defined as a duration of at least 4 months)
- PFS: the duration from the date of the first dose of study drug until the date of first documented evidence of progressive disease (or relapse for subjects who experience CR during the study) or death, whichever comes first, for subjects. Data from subjects who are progression-free and alive or have unknown status will be censored at the last tumor assessment
- OS: measured from the date of first dose of study drug to the date of the subject's death. If the subject is alive or the vital status is unknown, the subject's data will be censored at the date the subject was last known to be alive

Details for the PRO endpoints will be provided in a separate Statistical Analysis Plan.

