2.2. Analysis Sets

2.2.1. Efficacy Analysis Set(s)

2.2.1.1. Broad Panel Cohort

The alterations eligible for inclusion in the Broad Panel Cohort consist of target FGFR mutations and any FGFR fusion. The list of Target FGFR mutations eligible for the Broad Panel Cohort is

provided in Protocol Section 10.11. The Broad Panel Cohort will represent the primary cohort of interest for analysis. The efficacy analysis sets of the Broad Panel Cohort are specified below:

- The Treated Population will consist of all subjects (FGFR+) who received at least 1 dose of study drug. The Treated Population is the primary population for analyses of efficacy, baseline demographics and disease characteristics, and patient-reported outcome(s).
- The Response-evaluable Population will include all subjects (FGFR+) who satisfy the following criteria:
 - Met all eligibility criteria for the study;
 - Received at least 1 dose of study drug;
 - Had a baseline and at least 1 adequate post-treatment radiological disease evaluation, or had clinical signs or symptoms of disease progression, or died prior to the first posttreatment disease evaluation (these subjects will be considered non-responders). Adequate disease assessment is defined as having enough evidence to indicate that progression has or has not occurred.

The Response-evaluable Population will be used for the interim analysis, and supplementary efficacy analysis on key endpoints such as ORR and DOR.

- The Core Panel Cohort, which is a subgroup of the Treated Population in the Broad Panel Cohort with a select panel of pre-specified FGFR markers, will be assessed for efficacy as part of the primary analysis. The subset of FGFR markers was selected based on observed clinical activity in previous studies or a high level of recurrence of these alterations across tumor histologies; the subset of FGFR markers is outlined below:
 - FGFR3 mutations: S249C; Y373C; R248C; G370C
 - FGFR2 mutations: C382R
 - FGFR3 fusions: FGFR3-TACC3
 - FGFR2 fusions: FGFR2-BICC1; FGFR2-TACC2

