- EORTC QLQ-C30 global health status/quality of life subscale
- EQ-5D-5L utility score
- EQ-5D-5L VAS

Compliance rates for completion of EORTC QLQ-C30 and EQ-5D-5L at each time point will be generated.

The change from baseline in PRO endpoints at each time point will be summarized with descriptive statistics (N, mean, SD, median, and range [minimum and maximum]). The mean and standard deviation of change from baseline over time will be graphically presented with line plot.

A distribution-based method will be used to define worsening/improvement in EORTC QLQ-C30, i.e., half standard deviation away from the mean score at baseline. Time to worsening and time to improvement will be derived. Time to worsening will be estimated using Kaplan-Meir methods. Death due to disease progression will be considered as worsening. Subjects who have not met the definition of worsening will be censored at the last PRO assessment. Subjects without baseline assessment or post-baseline assessment will be censored at date of treatment start date.

In addition, PGIC and PGIS will be analyzed with descriptive statistics. In addition, change from baseline in PGIS will be summarized with descriptive statistics over time.

Peds FACT-Br (for subjects <18 years of age) will be analyzed for the Pediatric Cohort at the time of final analysis for the Pediatric Cohort.

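### SAP 5.3.5 censors unscanned subjects at first dose without excepting those who died; read literally, deaths before the first scan stop being PFS events

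*SAP*

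**What the plan says.** SAP 5.3.5 measures PFS from first dose "until the date of first documented evidence of progressive disease or death due to any cause, whichever occurs first". Four censoring sentences follow:

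- The general rule: "Subjects who are progression-free and alive or have unknown status will be censored at the last disease evaluation".
- The rule at issue: "Subjects with no baseline or no post-baseline disease evaluation will be censored at the date of first dose".
- Progression or death after the start of subsequent anti-cancer therapy is censored at the last evaluation before that therapy.
- The missed-evaluation rule: "Subjects with death or progressive disease after more than one missing disease evaluations will be censored", with the date set to the last evaluation free of progression.

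Protocol 9.4.2, like the endpoint table in Protocol section 3, has only one censoring rule for PFS: "Data from subjects who are progression-free and alive or have unknown status will be censored at the last tumor assessment". It has no first-dose rule.

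The plan foresees early deaths elsewhere. SAP 2.2.1.1 keeps in the Response-evaluable Population those who "died prior to the first posttreatment disease evaluation (these subjects will be considered non-responders". SAP 5.2.1 treats a subject without a post-baseline tumor assessment as a non-responder, and SAP 5.3.6 counts every death for OS.

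SAP 5.3.7 has a similar pair of statements for time to worsening on the QLQ-C30. Death due to progression is a worsening, yet "Subjects without baseline assessment or post-baseline assessment will be censored at date of treatment start date".

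**The concern.** A subject who dies unscanned at week 4 is a failure for ORR and for OS, and meets the PFS definition. Under a literal reading of the first-dose rule, the same subject adds no event and no follow-up to PFS. The subjects removed in this way are those who failed fastest, so the Kaplan-Meier curve can only move in the drug's favour.

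The study has a single arm, so the PFS curve will be read against outside figures, such as the median PFS values that Protocol 2.1 cites for existing second-line treatments. The rule also carries into the PFS analyses for Japan (SAP A.4), which are split into four smaller subgroups.

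**Working it through.** The documents state no expected median PFS, event count or power, so there is no planned figure to reproduce. The check compares the rules and then sizes the effect under stated assumptions.

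**Rules applied to an adult who dies with no post-baseline scan.** Protocol 8.2 sets the timing: "For adult subjects, disease assessments will be performed every 6 weeks (every 2 cycles) for the first 12 months".

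| Rule | Death before week 6 (no scan missed) | Death in weeks 6 to 12 (one scan missed) |
|---|---|---|
| PFS definition, SAP 5.3.5 | event | event |
| Missed-evaluation rule (needs more than one missed) | not triggered | not triggered |
| Protocol 3 and 9.4.2 | event | event |
| First-dose rule, read literally | censored day 1 | censored day 1 |

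**Size.** Let p be the share who die before the first scan with no evaluation, and let the remaining subjects have exponential PFS with median m.

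- Early deaths counted, after the first scan: S(t) = (1 − p) × 0.5^(t/m).
- Early deaths censored at first dose: S(t) = 0.5^(t/m).
- Landmark PFS is therefore inflated by 1/(1 − p).
- Setting the first curve to 0.5 gives a median of m × (1 + log2(1 − p)), so the reported median is too high by the factor 1/(1 + log2(1 − p)).

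For illustration, m is 4.0 months (the second-line glioblastoma figure in Protocol 2.1) or 5.6 months (the earlier erdafitinib cholangiocarcinoma cohort in Protocol 2.2.1). Both are assumptions here.

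| p (assumed) | 1 + log2(1 − p) | Factor | Median with deaths counted, m = 4.0 | Median with deaths counted, m = 5.6 |
|---|---|---|---|---|
| 3% | 0.956 | 1.046 | 3.82 | 5.35 |
| 5% | 0.926 | 1.080 | 3.70 | 5.19 |
| 10% | 0.848 | 1.179 | 3.39 | 4.75 |

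**Check by a Kaplan-Meier calculation** with 240 subjects, all followed to an event.

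- At p = 5% (12 subjects), the literal rule leaves 228 events instead of 240. The median reads 4.03 instead of 3.68 months, or 5.64 instead of 5.15. Three-month PFS reads 0.597 instead of 0.567, or 0.689 instead of 0.654.
- At p = 10% (24 subjects), the median reads 4.03 instead of 3.37 months, or 5.64 instead of 4.72.

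These medians differ from the formula by 0.02 to 0.04 months, which reflects the steps of a finite curve.

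**Is the range of p plausible?** Protocol 2.1 cites median survival of 7 to 8 months (head and neck) and 9 months (glioblastoma) in second-line disease. Six weeks is 42/30.44 = 1.38 months. Under a constant hazard, 1 − 0.5^(1.38/7.5) is about 12% and 1 − 0.5^(1.38/9) is about 10% dead by the first adult scan. This counts all deaths by then, scanned or not. Entry limited to ECOG 0 or 1 should lower it. It shows only that a few percent is not far-fetched.

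**The case against.** The strongest reply is that the sentence can be read more narrowly. It follows directly on the rule for subjects alive and progression-free or of unknown status, and may only supply their censoring date when no evaluation exists. The two later sentences that do censor deaths both name death; this one does not. SAP 5.1.2 also leaves further data-handling rules to a DPS that is not among the documents, and an exception could be there. This stands in part: a reader might infer that the SAP definitely discards every early death, and the text does not settle that. But the sentence is unconditional, no order of precedence is given, and nothing in the SAP supplies the exception.

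Second, PFS is descriptive, with no hypothesis, alpha or power, and no success or futility decision uses it. This stands in full.

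Third, an early death need not be unscanned. Protocol 8.2 allows extra scans and asks sites to document objective progression after symptomatic deterioration. This stands, and it lowers p.

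Two wider claims are tempting but not supported:

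- A reader might infer that time to worsening on the QLQ-C30 is distorted to the same degree. The questionnaire is scheduled at Cycle 1 Day 14, so mainly deaths before about that day, or missed forms, are affected.
- A reader might infer that every child's first scan is at week 12. Protocol 8.2 sets 12-weekly assessments for pediatric subjects, but Protocol 8.2.1.2 schedules brain MRI every 6 weeks for all subjects with primary brain tumors. The exposed window is longer only for children actually scanned every 12 weeks.

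**Conclusion.** The point holds as a defect of wording with a predictable direction. As written, SAP 5.3.5 permits, and on a literal reading requires, day-1 censoring of deaths that its own definition and the protocol make events. The bias favours the drug in any cohort where such a death occurs, and is nil where none does. The overstatement of the median, about 5%, 8% and 18%, rests on three assumptions: an early-death share of 3%, 5% and 10%, all of those deaths unscanned, and exponential PFS in the rest. The true share is not in the documents.

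It would be wrong to infer that the study's main conclusion is at risk. ORR counts these subjects as non-responders and OS counts their deaths.

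**What to change.** Replace the sentence in SAP 5.3.5 with:

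> A subject who has not died and who lacks a baseline or any post-baseline disease evaluation is censored on the first-dose date. A death before the first post-baseline evaluation is a PFS event on the day of death, unless subsequent anti-cancer therapy had already begun or more than one scheduled evaluation had been missed. In those two cases the subject is censored on the first-dose date.

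The two exceptions keep the subsequent-therapy and missed-evaluation rules in force, so that no subject is both an event and censored.

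Apply this at the final analysis, where Protocol 9.4.3.2 updates all efficacy results, and to any rerun of adult PFS. The Amendment 5 rationale in Protocol 10.14 records that the adult primary analysis is complete. State how early deaths were handled there.

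As a minor parallel, clarify in SAP 5.3.7 that death due to disease progression counts as worsening even without a post-baseline PRO.

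The cost is SAP wording and a small derivation change, with no new data. If the literal rule was coded, reported PFS will become somewhat less favourable.

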8.1.2. Treatment Phase

The Treatment Phase will begin with the administration of the first dose of erdafitinib and will continue until disease progression, intolerable toxicity, withdrawal of consent, decision by the investigator to discontinue treatment, or the end of data collection timepoint has been achieved. Subjects assessed with progressive disease, but for whom the treating physician strongly believes that continuation of study treatment will provide clinical benefit, may be allowed to continue treatment with erdafitinib after consultation with the medical monitor (please see guidelines in Section 8.2.2). The subject will continue to follow procedures as outlined in the Schedule of Activities and receive treatment until the treating physician and the medical monitor agree that further continuation of treatment is no longer providing benefit to the subject.

Throughout the Treatment Phase, the investigator will assess response to therapy using RECIST Version 1.1 or RANO. Efficacy evaluations are described in Section 8.2. For subjects who discontinue study therapy without documented disease progression, every effort should be made to continue monitoring their disease status by tumor imaging according to the imaging schedule, until (1) the start of new anti-cancer treatment, (2) disease progression, (3) withdrawal of consent, (4) death, or (5) the end of the study, whichever occurs first.

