5.2.2. Estimand

The primary estimand, the main clinical quantity of interest to be estimated in this study, is defined by the following four components (ICH E9 (R1) Addendum, 2018):

- Population: subjects with advanced solid tumors and target FGFR Gene Alterations.
- Variable: subject responder status (responder – BOR of CR or PR; otherwise – non-responder).
- Intercurrent events: treatment discontinuation and subsequent anti-cancer therapy. The treatment policy strategy will be applied to account for the treatment discontinuation. That is, the value for the variable of interest is used regardless of whether the treatment discontinuation occurs. The while-on-treatment policy will be applied to account for subsequent anti-cancer therapy. That is, only the value for the variable of interest before the subsequent anti-cancer therapy will be used. For instance, if a subject discontinued study treatment but did not start subsequent anti-cancer therapy, the subject's responder status/tumor assessment will be used as if the subject is still on treatment regardless of the treatment discontinuation (i.e. the treatment policy). But if a subject started subsequent anti-cancer therapy, no matter whether the subject has discontinued treatment or not, the subject's responder status/tumor assessment after the subsequent anti-cancer therapy will not be used in the analysis (the while-on-treatment policy).
- Population-level summary: ORR assessed by IRC.

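### SAP 5.3.5 and 5.3.2 limit PFS and DOR follow-up at subsequent therapy only for subjects who later have an event, so any evaluations after that therapy would bias both curves upward

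*SAP*

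**What the plan says.** SAP 5.3.5 has two PFS censoring sentences that bear on this point.

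- Event-free subjects: "Subjects who are progression-free and alive or have unknown status will be censored at the last disease evaluation". Subsequent therapy is not mentioned.
- Subjects with a later event: "Subjects who had a disease progression or death event after having started a subsequent anti-cancer therapy will be censored at the last disease evaluation before" that new treatment.

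SAP 5.3.2 has the same structure for DOR. Event-free subjects: "Subjects who are progression-free and alive or have unknown status will be censored at the last tumor assessment". Subjects with an event: "Subjects who had disease progression or death event but started a subsequent anti-cancer therapy before disease progression or death event will be censored"; their date is that of the final assessment preceding the new treatment.

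Protocol 9.4.2 gives only the event-free rule ("Data from subjects who are progression-free and alive or have unknown status will be censored at the last tumor assessment") and no subsequent-therapy rule.

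For ORR, SAP 5.2.2 is uniform: "But if a subject started subsequent anti-cancer therapy, no matter whether the subject has discontinued treatment or not", assessments after that therapy are not used.

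On imaging, Protocol 8.1.2 says that subjects who stop drug without progression continue scans "according to the imaging schedule, until (1) the start of new anti-cancer treatment, (2) disease progression", or until one of three further end points.

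**The concern.** Take two subjects who start another anti-cancer therapy at month 3 without progression, and suppose that both still have evaluations in the database afterwards. A progresses at month 8. B is event-free at a month-12 scan. Under SAP 5.3.5, A is censored at the last evaluation before month 3 and B at month 12. Their histories at month 3 are identical, and only the later outcome separates their censoring dates.

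Kaplan-Meier estimation requires that the censoring date not be chosen by looking ahead to the event. Here event-free time after another therapy is credited to erdafitinib, while events in the same period are removed. The study has a single arm (SAP 1.5), so there is no control group in which the error could cancel. The SAP gives no reason for using a different rule from the one it adopts for ORR.

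**Working it through.** **Nothing to reproduce.** The documents give no target, power or sample size for PFS or DOR, and no rate of subsequent therapy before progression.

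**Direction.** Each Kaplan-Meier factor is 1 − d/n, with d events and n at risk. Compare the written rule with a uniform rule that censors everyone at the last evaluation before subsequent therapy. Neither rule counts an event after that therapy, so d is the same at every event time. The written rule keeps event-free switchers at risk for longer, so n is the same or larger. The written curve therefore lies on or above the uniform curve at every time point. They coincide if no switcher has a later evaluation.

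**Can later evaluations exist?**

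- *Off drug:* scheduled imaging ends at new anti-cancer treatment (Protocol 8.1.2). The Follow-up Phase (8.1.4) records survival and subsequent therapy, not scans. B's last evaluation is then already the last one before the new therapy, and A and B get the same date.
- *On drug:* other antineoplastic agents are prohibited (Protocol 6.5.2, with a hormonal exception in 6.5.1). Localized palliative radiotherapy is permitted (6.5.1), and imaging continues on schedule (8.2.1.2). SAP 4.8 includes radiotherapy and cancer-related surgery in its subsequent-therapy summary. SAP 5.3.2 and 5.3.5 do not say which therapies trigger censoring.
- *Otherwise:* unscheduled scans are allowed (Protocol 8.2), and disallowed concomitant treatment is a listed deviation category (SAP 4.5).

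**Size.** A simulation of 400,000 subjects per setting compared the two rules. Inputs from the documents: 6-weekly scans (Protocol 8.2, here used throughout, although the plan moves to 12-weekly after 12 months) and at least 6 months of follow-up (Protocol 9.4.3.1). Everything else is assumed:

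- exponential time to progression, median 4, 6 or 9 months;
- exponential time to death, median 2.2 times that;
- uniform accrual over 18 months;
- a nominal p = 10%, 20% or 30% starting new therapy before an event, independently of progression risk;
- a share q of those subjects with later scans in the data.

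The therapy-start hazard is g = h·p/(1 − p), where h is the sum of the progression and death hazards. For median 6 and p = 0.20, h = ln 2/6 + ln 2/13.2 = 0.1155 + 0.0525 = 0.168 per month, so g = 0.168 × 0.20/0.80 = 0.042 per month. The realised share starting therapy was about 20%.

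| q | 12-month PFS, written minus uniform, over nine settings | Example (median 6, p = 20%) |
|---|---|---|
| 0 | 0.000 | 0.143 v 0.143 |
| 0.25 | +0.002 to +0.014 | 0.151 v 0.144 |
| 0.5 | +0.004 to +0.028 | 0.158 v 0.143 |
| 1 | +0.007 to +0.053 | 0.172 v 0.144 |

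The largest shift in the median was 4.46 v 4.14 months, about 0.3 months (median 6, p = 30%, q = 1). In most settings it did not move materially. DOR was not simulated separately; the argument on direction applies to it unchanged.

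**The case against.** The strongest objection is that conduct under the protocol largely prevents the problem. Off-drug imaging stops at new treatment, follow-up visits collect no scans, and concurrent anti-cancer drugs are prohibited on study drug. Other provisions also treat subsequent therapy as something that follows study treatment: the End-of-Treatment Visit precedes it (Protocol 8.1.3), and SAP 2.6 moves an imputed start date that falls earlier in the month of discontinuation to the discontinuation date. Palliative radiotherapy is listed as a permitted concomitant measure, and SAP 4.8 describes a summary table, not a censoring trigger. SAP 5.1.2 also defers other data handling rules, if any, to a separate document that is not available here.

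Most of this stands, and it rules out two stronger readings. A reader might infer that event-free subjects routinely continue to be scanned after new therapy, so that the curves are biased as a matter of course. The documents point the other way, and the remaining routes are narrow and unquantified. A reader might also take the on-drug wording in SAP 5.2.2 as a forecast that such cases will be common. It covers a contingency and predicts nothing.

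The objection does not rescue the wording. The rule gives the right date only if no later evaluations reach the database, and nothing in the PFS or DOR text ensures that.

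**Conclusion.** The rule is wrong as written in both sections: it conditions censoring on a later event and is inconsistent with SAP 5.2.2. Its practical effect runs from exactly zero, when no evaluations after subsequent therapy are in the data, to about 1 to 5 percentage points on 12-month PFS if every switcher continues to be scanned. With a quarter scanned it is about 0.2 to 1.4 points. These figures rest on assumed switching rates of 10% to 30%, exponential times and therapy start unrelated to progression risk. The direction follows from the risk sets and does not depend on those assumptions.

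A reader might infer that median PFS moves by a full scan interval. A separate run, with a median of 9 months and 19% switching, did show a jump from 9.7 to 11.0 months. That reflects events falling on a fixed scan grid and should not be relied on, given the shift of at most 0.3 months in the main runs.

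PFS and DOR are secondary endpoints summarised descriptively, so no test, alpha level, sample size or success rule is affected. This is a minor point, worth correcting because the change is small and the possible error runs in one direction only.

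**What to change.** In SAP 5.3.5 and 5.3.2, replace the subsequent-therapy sentence with a single rule: any subject who starts subsequent anti-cancer therapy before documented progression or death is censored at the last disease evaluation on or before that start, whether or not an event follows. Make the event-free sentence subject to this rule. State which therapies count as subsequent anti-cancer therapy for this purpose, in particular whether radiotherapy or surgery given while on study drug does.

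The cost is one sentence in each section plus the definition. No new data are needed. If no evaluations after subsequent therapy exist, the results do not change. If some do, later PFS and DOR estimates may become slightly less favourable.
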